#### 14.3.1.2 Onset of effect

Onset of effect is defined as at least 20 % reduction from baseline pain intensity on VAS, and the time to onset of effect for the first flare will be analyzed using a stratified log-rank test, with ULT use (yes, no) and BMI (<30.0, ≥30.0 kg/m^2) as stratification factors (see Section 18.19). Based on this model, the estimated hazard ratio (anakinra versus triamcinolone), 95 % confidence interval and p-value will be presented. Further, the hazard ratios for the comparisons of the 2 different anakinra dose groups versus triamcinolone will also be estimated, with corresponding 95 % confidence intervals and p-values.

The hazard ratio and its confidence interval will be estimated based on Peto's method:

$$HR = \exp(U/V)$$

$$95\% \text{ CI for HR} = (\exp\{U/V - 1.96/\sqrt{V}\}, \exp\{U/V + 1.96/\sqrt{V}\})$$

Where  $U = \sum (d_{1i} - e_{1i})$  is the log-rank test statistic (with  $d_{1i}$  and  $e_{1i}$  the observed and expected events in group 1) and  $\sqrt{V}$  the SD of the log-rank test statistic as produced in the PROC LIFETEST output. This approach will be adapted for a stratified approach by using the U and V statistics obtained directly from the LIFETEST having added a STRATA term for each of the

stratification variables. Patients with only baseline values and patients with no values will be censored at baseline, i.e. will not be included in the analysis.

Time to onset of effect will also be presented graphically for the two dose groups of anakinra and triamcinolone.

In addition, the number and proportion of patients with onset of effect in the different treatment groups up to 6, 12, 24, 48 and 72 hours will be presented. The percentages will be based on the number of patients in the ITT population.

The number and percentage of patients with and without onset of effect within 24 hours versus the number and percentage of patients with and without response within 72 hours will also be tabulated.

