## **7 Sample size determination**

Up to totally 169 patients can be randomized in the study. Initially 159 patients will be randomized, 53 to triamcinolone and 106 to anakinra (53 to 100 mg and 53 to 200 mg). As described in section 4.2, up to a maximum of 10 extra patients can be randomized.

The sample size calculation is based on the change in pain intensity on a VAS 0 to 100 mm from baseline to the average over 24 to 72 hours. A sample size of 106 patients randomized to anakinra and 53 patients randomized to triamcinolone is required to ensure a power of 80 % to reject the null hypothesis of no difference between anakinra and triamcinolone assuming a true difference of 12 mm on VAS mean change and a SD of 25 mm when using a 2-sided test with a significance level of 5 %.

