## **9 General considerations for statistical analysis**

All statistical tests will be 2-sided and performed using a 5 % significance level, if not stated otherwise. Results will be presented as the point estimate for each treatment group, the estimated difference between groups, the associated 95 %, 2-sided confidence interval and p-value. P-values from statistical analyses will be presented to 3 decimal places with values below 0.001 displayed as <.001 and confidence intervals will be presented to one more decimal place than the raw data.

Continuous data will be summarized using descriptive statistics: n, mean, SD, median, minimum and maximum, unless otherwise stated. Minimum and maximum will be presented to the same number of decimal places as the raw data and mean, SD, standard error of the mean and median will be presented to one more decimal place than the raw data.

Categorical data will be summarized using counts and percentages. Percentages will be suppressed when the count is zero, however the category will still be displayed. The denominator for all percentages will be the number of patients within the treatment group for the population of interest, unless otherwise indicated. Percentages will be presented to one decimal place.

Statistical analyses will be performed using SAS software, Version 9.1 or later (SAS Institute Inc, Cary, North Carolina, United States).

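### The Peto one-step hazard ratio is biased for the 2:1 combined-anakinra comparison when the effect is large; a stratified Cox estimate would remove this at little cost

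*SAP*

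**What the plan says.** SAP 14.3.1.2 to 14.3.1.5 compare four event times (onset of effect, response, resolution of pain, first rescue medication) with a log-rank test stratified by ULT use and BMI. From this, "the estimated hazard ratio (anakinra versus triamcinolone), 95 % confidence interval and p-value will be presented". In addition, "the hazard ratios for the comparisons of the 2 different anakinra dose groups versus triamcinolone will also be estimated".

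The estimator is set out in 14.3.1.2: "The hazard ratio and its confidence interval will be estimated based on" Peto's method. The formula is HR = exp(U/V), with limits exp(U/V ± 1.96/√V). U is observed minus expected events and √V is the standard deviation of the log-rank statistic. For the strata, "This approach will be adapted for a stratified approach by using the U and V statistics obtained directly from the LIFETEST". Sections 14.3.1.3 to 14.3.1.5 refer back to this method.

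The plan therefore yields 4 × 3 = 12 first-flare hazard ratios. Four are combined comparisons of 106 v 53 and eight are dose-level comparisons of 53 v 53 (group sizes from SAP section 7).

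Protocol 9.3.4.2 to 9.3.4.5 ask for a hazard ratio and interval alongside the stratified log-rank test but name no estimator. Neither document states an expected hazard ratio or event rate for these endpoints.

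**The concern.** exp(U/V) is a single step from a hazard ratio of 1, using the variance that holds when there is no effect. With equal risk sets the leading error cancels. With two anakinra patients at risk for every triamcinolone patient it does not, and the estimate is pulled down on both sides of 1: values below 1 are exaggerated and values above 1 are shrunk.

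The consequence depends on the endpoint. For rescue medication a hazard ratio below 1 favours anakinra, so a strong benefit would be overstated with an interval that is too short. For onset, response and resolution a hazard ratio above 1 favours anakinra, so the same pull generally works against it.

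The combined and dose-level hazard ratios also carry different biases because their allocations differ, yet they will be read side by side.

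**Working it through.** **The plan's own figure.** The only related figure is the sample size for the primary endpoint (12 mm, SD 25 mm, two-sided 5%). SE = 25 × √(1/106 + 1/53) = 4.21; 12/4.21 = 2.85; 2.85 − 1.96 = 0.89, which gives 81.4% power (80.9% with the t distribution). The stated 80% is reproduced. Nothing in it depends on the hazard-ratio formula.

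**A hand check of the formula.** Take one event when a share p of those at risk is on anakinra, with true hazard ratio θ. The expected contribution to U is pθ/(pθ + 1 − p) − p, and the contribution to V is p(1 − p). Early in follow-up p = 2/3 and V = 0.222 for the combined comparison.

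- θ = 0.5: (0.500 − 0.667)/0.222 = −0.75; exp(−0.75) = 0.47.
- θ = 0.8: (0.615 − 0.667)/0.222 = −0.23; exp = 0.79.
- θ = 1.5: (0.750 − 0.667)/0.222 = 0.375; exp = 1.46.
- θ = 2: (0.800 − 0.667)/0.222 = 0.60; exp = 1.82.
- At 1:1 (p = 1/2, V = 0.25): θ = 0.5 gives exp(−0.667) = 0.51 and θ = 2 gives exp(0.667) = 1.95.

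So if both doses had a true hazard ratio of 0.5, the pooled value (0.47) would lie below both dose values (0.51).

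The same check explains the coverage. At θ = 0.5 the true variance per event is 0.5 × 0.5 = 0.25 against the 0.222 assumed. The true SE is then √(0.25/0.222) = 1.06 times the one used, and the interval is too short. At θ = 2 the true variance is 0.8 × 0.2 = 0.16, and the ratio is √(0.16/0.222) = 0.85. The interval is wider than needed, which offsets the shift.

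As events accrue at θ = 0.5, p rises above 2/3 and the downward pull grows. At θ = 2, p falls and the shrinkage eases.

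**Simulation of the full formula.** 106 v 53, four equal strata, proportional hazards, continuous times, 6,000 runs per cell. Assumed inputs: the true hazard ratio, the equal strata, and control event fractions of 40 / 70 / 95%. Estimates are geometric means.

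| True HR | Peto HR | Peto coverage, % | Cox HR | Cox coverage, % |
|---|---|---|---|---|
| 0.5 | 0.466 / 0.456 / 0.452 | 92.3 / 90.8 / 89.0 | 0.501 / 0.498 / 0.500 | 95.2 / 95.0 / 95.5 |
| 0.67 | 0.649 / 0.645 / 0.639 | 93.7 / 92.7 / 92.9 | 0.672 / 0.669 / 0.664 | 95.5 / 94.7 / 95.5 |
| 0.8 | 0.790 / 0.790 / 0.781 | 94.6 / 94.0 / 93.3 | 0.805 / 0.802 / 0.793 | 95.6 / 95.1 / 94.6 |
| 1.25 | 1.245 / 1.232 / 1.239 | 95.7 / 95.3 / 95.3 | 1.271 / 1.247 / 1.251 | 95.2 / 95.0 / 94.9 |
| 1.5 | 1.459 / 1.462 / 1.465 | 96.0 / 96.2 / 95.5 | 1.515 / 1.500 / 1.495 | 95.1 / 95.4 / 95.1 |
| 2 | 1.862 / 1.905 / 1.914 | 95.8 / 95.3 / 94.6 | 2.023 / 2.017 / 2.008 | 95.0 / 94.9 / 94.8 |
| 2.5 | 2.220 / 2.295 / 2.332 | 93.5 / 93.1 / 92.9 | 2.522 / 2.494 / 2.515 | 95.0 / 94.6 / 94.5 |

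A separate simulation (2,000 runs) gave 0.44 to 0.46 with 88 to 92% coverage at a true 0.5, and 2.58 to 2.75 with 90 to 93% at a true 3. Stratified Cox stayed within about 2% of the truth with 94 to 96% coverage.

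**Rescue-like case** (about 45% of controls with an event, 1,500 runs). A true 0.5 gave Peto 0.465 (91.3%) and Cox 0.503 (94.7%). A true 0.6 gave 0.57 (93.3%) and 0.60 (95.3%).

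**Dose-level comparisons** (53 v 53, 1,500 runs). From 0.4 to 2 the estimate was within about 4% of the truth, with 93 to 96% coverage. At 2.5 to 3 the bias was up to +6%, with 91 to 94% coverage.

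**Heavy ties** (times grouped at the nominal assessments, 3,000 runs, at least 95% of controls with an event). A true 2 gave 2.04 to 2.13 with about 95% coverage, so the shrinkage reversed. A true 0.5 still gave 0.42 to 0.44 with 88 to 90%. The Cox fits in these runs used Breslow ties and gave 1.87 and 1.78 at a true 2, which is why the tie method must be stated. Efron ties were not run on grouped times.

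**The case against.** The best defence is coherence. The interval U/V ± 1.96/√V excludes zero exactly when |U|/√V exceeds 1.96, so interval and log-rank p-value always agree. The protocol also ties the hazard ratio to the log-rank analysis. That is a genuine advantage, and the proposed change gives it up near p = 0.05.

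The second defence is scale. These are secondary endpoints of an exploratory Phase 2 study against an active comparator chosen for good pain reduction (Protocol 7.2.3), so halved or tripled hazards are not an obvious default. In the rescue-like case at a true 0.5, expected events are 0.45 × 53 + (1 − √0.55) × 106 ≈ 24 + 27 = 51. The SE of the log hazard ratio is then about 1/√(51 × 0.222) = 0.30, and the shift log(0.5/0.465) = 0.07 is about a quarter of it. This stands as a limit on importance.

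Third, pain is scored on a schedule, so event times may cluster, and ties can remove the shrinkage above 1. This stands in part: SAP 18.19 to 18.21 use actual measurement times, which limits ties, and 18.22 uses the recorded date and time of rescue. Ties do not cure the exaggeration below 1.

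Fourth, rescue is allowed only after the 24-hour assessment, so a constant hazard from time zero is unrealistic. This carries little weight, because both estimators use only the order of event times. What matters is proportional hazards and the event fraction.

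A reader might go further and infer that the stated 95% intervals fail in general, or that the method favours anakinra throughout. Neither follows. Coverage at 1.25 to 2 is nominal, eight of the twelve hazard ratios are 1:1 and little affected, and for three of the four endpoints the bias generally runs against anakinra.

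**Conclusion.** The point holds in limited form. For the four 2:1 combined comparisons the Peto estimate is materially biased only when the effect is large. Under-coverage is clear only at hazard ratios of about 0.67 or lower and about 2.5 or higher.

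The one place where it could flatter anakinra is time to rescue medication in the combined comparison, and only if the effect is strong. The log-rank p-values stand, because V is the right variance under the null hypothesis.

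All sizes rest on assumed hazard ratios and event fractions and on proportional hazards. The result for values above 1 also rests on near-continuous event times. The documents give no basis for saying which of these hazard ratios will apply, so they do not show that any reported result will be wrong.

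**What to change.** In SAP 14.3.1.2 to 14.3.1.5, take the hazard ratio and 95% interval from a Cox model stratified by ULT use and BMI, with Efron handling of ties, for combined anakinra and for each dose against triamcinolone. Keep the stratified log-rank p-value, and state that it is the p-value reported.

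The cost is a few lines of SAP text and one standard procedure call. The protocol names no estimator, so its text need not change; a line in SAP section 5 could record the choice. The drawback is that the Cox interval and the log-rank p-value may disagree marginally when p is near 0.05.

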### **14.3.1.3 Response**

Response is defined as at least 50 % reduction from baseline pain intensity on VAS, and the time to response for the first flare will be analyzed using a stratified log-rank test, with ULT use (yes, no) and BMI ( $<30.0$ ,  $\geq 30.0$  kg/m^2) as stratification factors (see Section 18.20). Based on this model, the estimated hazard ratio (anakinra versus triamcinolone), 95 % confidence interval and p-value will be presented. Further, the hazard ratios for the comparisons of the 2 different anakinra dose groups versus triamcinolone will also be estimated, with corresponding 95 % confidence intervals and p-values.

The hazard ratio and its confidence interval will be estimated based on Peto's method (see Section 14.3.1.2). Patients with only baseline values and patients with no values will be censored at baseline, i.e. will not be included in the analysis.

Time to response will also be presented graphically for the two dose groups of anakinra and triamcinolone.

In addition, the number and proportion of responders in the different treatment groups at 24, 48 and 72 hours, Day 8 and Day 15 will be presented. The percentages will be based on the number of patients in the ITT population.

The number and percentage of patients with and without response within 72 hours versus the number and percentage of patients with and without onset within 24 hours will also be tabulated.

### **14.3.1.4 Resolution of pain**

Resolution of pain is defined as  $<10$  mm in patient-assessed pain intensity on VAS, and the time to resolution for the first flare will be analyzed using a stratified log-rank test, with ULT use (yes, no) and BMI ( $<30.0$ ,  $\geq 30.0$  kg/m^2) as stratification factors (see Section 18.21). Based on this model, the estimated hazard ratio (anakinra versus triamcinolone), 95 % confidence interval and p-value will be presented. Further, the hazard ratios for the comparisons of the 2 different anakinra dose groups versus triamcinolone will also be estimated, with corresponding 95 % confidence intervals and p-values.

The hazard ratio and its confidence interval will be estimated based on Peto's method (see Section 14.3.1.2). Patients with only baseline values and patients with no values will be censored at baseline, i.e. will not be included in the analysis.

Time to resolution of pain will also be presented graphically for the two dose groups of anakinra and triamcinolone.

In addition, the number and proportion of patients with resolution of pain in the different treatment groups at 72 hours, Day 8 and Day 15 will be presented. The percentages will be based on the number of patients in the ITT population.

#### **14.3.1.5 Rescue medication**

Time to first intake of rescue medication during the first flare will be analyzed using a stratified log-rank test, with ULT use (yes, no) and BMI ( $<30.0$ ,  $\geq 30.0$  kg/m^2) as stratification factors (see Section 18.22). Based on this model, the estimated hazard ratio (anakinra vs. triamcinolone), 95 % confidence interval and p-value will be presented. Further, the hazard ratios for the comparisons of the 2 different anakinra dose groups versus triamcinolone will also be estimated, with corresponding 95 % confidence intervals and p-values.

The hazard ratio and its confidence interval will be estimated based on Peto's method (see Section 14.3.1.2). Patients with only baseline values and patients with no values will be censored at baseline, i.e. will not be included in the analysis.

Time to first intake of rescue medication will also be presented graphically for the two dose groups of anakinra and triamcinolone.

In addition, the proportion and number of patients who took rescue medication from the first IMP administration up to 12 hours, >12 to 24 hours, >24 to 48 hours, >48 to 72 hours, >72 hours to Day 8, and >Day 8 to Day 15 in the different treatment groups will be presented. The proportion and number of patients with 0, 1, 2, 3 or more than 3 occasions with rescue medications as well as descriptive statistics for number of occasions will be presented in the same time intervals. Multiple occurrences of rescue medication within 15 minutes will only count as one occurrence.

The type of rescue medication taken will also be summarized in the same time intervals per flare.

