7.5.5.4 Use of rescue medication

Patients who have difficulty in tolerating their pain are allowed to take rescue medication as needed after the 24-hour post-dose pain assessment but not within 6 hours before the 48- and 72-hour post-dose pain assessments.

Rescue medication can be used at the discretion of the investigator and should be prescribed according to the product label; contraindications, interactions and precautions.

Permitted rescue medication includes paracetamol/acetaminophen (up to 1000 mg 4 times daily) and/or codeine (up to 50 mg 4 times daily) or short acting tramadol (up to 100 mg 4 times daily).

Topical ice/cold packs may also be used as rescue therapy.

However, patients will be permitted to continue thrombosis prophylaxis with low dose acetyl salicylic acid (≤ 325 mg/day).

At the discretion of the investigator, patients still having insufficient relief with above drugs after the 72-hour post-dose pain assessment are allowed to take oral prednisone, prednisolone or equivalent at a dose up to 0.5 mg/kg per day for a maximum of 5 days.

Subsequent flares occurring before Day 15 of the latest flare will be treated with permitted rescue medication.

The name, dose, date and time of all rescue medication taken at site will be recorded in the eCRF at Visit 1 to 4 of each flare. Rescue medication taken at home between Visit 1 and 4 of each flare will be recorded in the patient diary.

7.5.5.5 Clinical signs of the most affected joint (index joint tenderness, swelling and erythema)

The investigator will assess the tenderness (on the basis of palpation or passive motion) of the index joint on a 4-point Likert scale (0=no pain, 1=mild/patient states there is pain when touched, 2=moderate/patient states there is pain and winces, 3=severe/patient states there is pain, winces and withdraws).

The investigator will assess the swelling of the index joint on a 4-point Likert scale (0=no swelling, 1=mild swelling, 2=moderate swelling, 3=severe swelling or bulging beyond joint margins).

The investigator will assess erythema of the index joint as either “present” or “absent”.

For each flare, assessments of joint tenderness, swelling and erythema will be performed and recorded in the eCRF at baseline, 72 hours, Day 8 and Day 15.

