9.3.10 Handling of missing data

Patients should continue in the study even if study treatment is withdrawn and every effort should be made to complete the assessments according to the protocol. The evaluation of patient-assessed pain using VAS and Likert scales have repeated assessment time points and repeated measures models will be used to handle missing data, i.e. no imputation is needed. To evaluate the robustness of this model for the primary endpoint, a tipping point analysis will be used for performing sensitivity analysis under the MNAR assumption (see 9.3.3.1 for details). For the secondary time-to-event analyses, patients who do not have an event at the time for analysis will be censored at the last time point with recorded information. For other secondary endpoints the analyses will be based on observed data. Details will be fully described in the SAP.

10 Data collection, handling and record keeping

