### 8.1 Intention-to-treat (ITT)

The ITT population is the primary analysis population for the primary and secondary efficacy endpoints, comprising all randomized patients grouped according to randomized treatment and stratum. Presentations of efficacy endpoints for subsequent flares will also be based on the ITT population.

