### **9.1 Handling of missing data and outliers**

Patients should continue in the study even if study treatment is withdrawn and every effort should be made to complete the assessments according to the protocol. The evaluation of patient-assessed pain using VAS and Likert scales have repeated assessment time points and repeated measures models will be used to handle missing data, i.e. no imputation is needed. To evaluate the robustness of this model for the primary endpoint, sensitivity analyses including multiple imputation methods will be performed (see Section 14.1.2). For the secondary time-to-event analyses, patients who do not have an event at the time for analysis will be censored at the last

time point with recorded information. For other secondary endpoints the analyses will be based on observed data.

In case of missing or incomplete dates or times, no imputations will be made in the listings of data. Rules on how to handle partially or completely missing dates or times in calculations are described in Section 18.

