## **18.22 Time to rescue medication**

Intake of rescue medication is recorded by the patient using the eDiary:

101 = Acetaminophen

102 = Paracetamol

103 = Acetaminophen/Codeine

104 = Paracetamol/Codeine

105 = Codeine

106 = Tramadol

(107 = Ice/cold-pack will not be counted as rescue in the time to rescue calculation)

108 = Other (non medicinal products will not be counted as rescue)

If other is selected the type will be recorded in the Rescue Medication in the eCRF. Patients still having insufficient relief with the rescue medication listed above after the 72 hour assessment are allowed to take glucocorticoids which can be recorded in the Rescue Medication form or Concomitant Medication form in the eCRF. If a patient has taken glucocorticoids, but has no earlier intake of rescue medication from the list, the glucocorticoid intake will be counted as rescue.

The date and time when the first rescue medication is taken in either system will be used in the calculation of time to intake of rescue medication, defined as (in hours):

*Date/time of intake of first rescue medication – date/time of intake of first IMP*

In case of incomplete or missing date and/or time for either occasion, the following rules will be applied:

- If the minute is missing, the time will be set to the full hour before, i.e. HH:00. If this imputation gives a time point that is prior to the first dose of IMP, the time will be set to the same time point as the first IMP injection.
- If both the hour and minutes are missing, the time will be set to 00:00.
- In the event of missing date, timing of rescue medication cannot be assessed and this recording will not be included in the analysis.
- For glucocorticoids captured as concomitant medication where only date and no timing information is available time is set to 00:00

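### The time-to-rescue analysis carries over a VAS exclusion rule that has no defined meaning for rescue medication and, on two of three readings, could bias the hazard ratio

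*SAP*

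**What the plan says.** SAP 14.3.1.5 analyses time to first rescue intake in the first flare by a stratified log-rank test with a Peto hazard ratio, for combined anakinra and for each dose against triamcinolone. It then adds: "Patients with only baseline values and patients with no values will be censored at baseline, i.e. will not be included in the analysis".

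The same sentence stands in SAP 14.3.1.2 (onset: "values and patients with no values will be censored at baseline, i.e. will not be included in the analysis"), 14.3.1.3 (response) and 14.3.1.4 (resolution). All three are defined on VAS scores.

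The rescue event is defined differently. SAP 18.22 says: "The date and time when the first rescue medication is taken in either system will be used in the calculation". The two systems are the eDiary and the eCRF. Protocol 7.5.5.4 adds: "The name, dose, date and time of all rescue medication taken at site will be recorded in the eCRF". Glucocorticoid rescue sits in eCRF forms too: "glucocorticoids which can be recorded in the Rescue Medication form or Concomitant Medication form in the eCRF" (SAP 18.22).

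The general rule for the secondary time-to-event endpoints is in Protocol 9.3.10, repeated in SAP 9.1: "patients who do not have an event at the time for analysis will be censored at the last time point with recorded information". The ITT population is defined as "comprising all randomized patients grouped according to randomized treatment and stratum" (SAP 8.1).

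**The concern.** A VAS endpoint has a baseline score and later scores, so a patient with nothing after baseline contributes no follow-up and time-0 censoring is natural. Rescue has no baseline score. A patient either has an intake record or does not, and having none is the favourable outcome. The sentence therefore has no plain meaning for this endpoint, and SAP 18.22, which gives imputation rules for dates and times, gives no censoring rule to settle it.

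At stake is a named secondary objective reported with a hazard ratio, confidence interval and p-value for three comparisons. A programmer who follows the sentence literally could remove the patients who did best, or discard events that are on file.

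**Working it through.** **The plan's own figure.** The documents give no rescue rate, event count, hazard ratio or power for time to rescue. The only stated figure is the primary sample size, which reproduces. With 53 and 106 patients, difference 12 mm and SD 25 mm, SE = 25 × √(1/53 + 1/106) = 4.21, 12/4.21 = 2.85, and power = Φ(2.85 − 1.96) = 0.81 against the stated 80%. The rescue rule does not touch it.

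**Three readings of the sentence**

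- *A: no rescue record.* Every non-user is excluded and only users remain. This contradicts Protocol 9.3.10 and SAP 9.1.
- *B: no post-baseline VAS.* A patient with rescue recorded in the eCRF but no post-baseline VAS is excluded although the event is known.
- *C: no post-dose rescue information from either system.* The patient has no follow-up, and time-0 censoring agrees with the general rule.

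**Reading A.** Assumptions, none from the documents: exponential times to rescue, follow-up to Day 15 taken as 336 h, 53 against 106 patients, HR = exp(U/V), unstratified.

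Take 60% rescue use on triamcinolone and 40% on anakinra:

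- True HR = ln(1 − 0.40)/ln(1 − 0.60) = 0.511/0.916 = 0.56.
- Expected users: 53 × 0.60 + 106 × 0.40 = 31.8 + 42.4 = 74.2. Patients removed: 159 − 74.2 = 84.8, or 53%.
- Simulated, all patients kept: HR about 0.52, power about 69%.
- Simulated, users only: HR about 0.88, power about 7%.

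Repeat runs vary in the second decimal of the HR and by a point or two in power, so about 0.5 against about 0.9 is the right precision.

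Holding the true HR at 0.60 and varying rescue use on triamcinolone (1,500 trials each):

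| Rescue use, triamcinolone | HR, all kept | Power | HR, users only | Power |
|---|---|---|---|---|
| 30% | 0.57 | 36% | 0.93 | 6% |
| 50% | 0.57 | 51% | 0.92 | 6% |
| 70% | 0.57 | 67% | 0.87 | 11% |

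The mechanism is simple: among patients who all have the event within the window, the times look much alike in both arms. With a true HR of 1.00 the users-only rejection rate stays at 5% to 7%. Reading A attenuates; it does not create false positives.

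**Reading B.** Assumptions: 50% rescue use on triamcinolone and 10 patients excluded. Ten is borrowed for illustration from the number of extra randomizations allowed for missing primary data (Protocol 7.3.6); it is not a cap on such patients. With all patients kept and a true HR of 0.60, the estimate is about 0.57.

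| Excluded patients (triamcinolone, anakinra) | HR, true 0.60 | HR, true 1.00 (rejection rate) |
|---|---|---|
| 3 and 7, irrespective of rescue use | 0.58 | 1.00 (5%) |
| 3 and 7, all rescue users | 0.51 | 0.96 (6%) |
| 10 and 0, all rescue users | 0.85 | 1.38 (25%) |
| 0 and 10, all rescue users | 0.42 | 0.87 (10%) |

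The last two rows are deliberate extremes. The direction depends on which arm loses users.

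**Reading C.** No bias beyond ordinary loss of information.

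**The case against.** A reader might infer that the plan drops every patient who took no rescue and so biases the hazard ratio outright. The documents do not support that.

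- The general rule in Protocol 9.3.10 and SAP 9.1 covers the secondary time-to-event endpoints, of which this is one, and it keeps non-users at risk.
- In the VAS sections the sentence cannot mean that no event occurred. A patient with scores who never responds has values and is censored later. Carried over with the same sense, it points to missing post-dose data, which is close to reading C.
- SAP 14.3.1.5 itself tabulates patients with 0 occasions of rescue, so zero is treated as an outcome and not as missing.
- A difference in rescue use would not vanish from the report: the same section gives numbers and proportions of patients taking rescue by interval to Day 15.
- VAS scores and home rescue use share one diary. Many patients without VAS may lack home rescue data too, which keeps reading B small.
- The rescue rates behind the size estimates are assumptions, and they posit a sizeable benefit.

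All of this stands, and it makes reading A an unlikely intention and the bias conditional. It does not rescue the sentence. The SAP does not say that the general rule overrides an endpoint-specific one. The reference to baseline values cannot apply to rescue on any reading. Rescue taken at site and glucocorticoids reach the eCRF independently of the diary, so reading B would still discard known events.

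**Conclusion.** The sentence is wrong as written for this endpoint: it is a misfitting stated rule, not merely missing detail. Whether it biases the result depends on how it is programmed. Under assumed rescue use of 40% against 60%, dropping non-users would move the hazard ratio from about 0.5 to about 0.9 and power from about 69% to about 7%; across the other assumed rates the pattern is the same. The VAS reading would probably affect few patients, with effects from none to large and no predictable direction. The third reading does no harm. The point is confined to one secondary endpoint without multiplicity control; the primary analysis and the sample size of 159 are untouched.

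**What to change.** Replace the sentence in SAP 14.3.1.5 with:

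> *Patients without rescue intake are censored at the last time point with recorded rescue information (eDiary or eCRF), at the latest Day 15. Only patients with no post-dose rescue information from either source are censored at time 0, and their number is reported by arm. Availability of VAS values plays no role.*

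Two additions are needed.

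- Say that a diary entry or visit at which rescue use was reviewed and none reported counts as recorded information. Otherwise the ambiguity returns.
- State how randomized patients who never received IMP are handled. SAP 18.22 measures time from first IMP while the ITT population includes everyone randomized. SAP 18.16 has a rule for undosed patients for pain scores, but 18.22 has none for rescue.

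The cost is SAP wording only, with no new data and no change to sample size. SAP 6.1 requires the SAP to be final before the first database lock and unblinding, and the change belongs before that point. Made later, it could look data-driven.
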